**Handling of missing date information for AEs:**

1. The term missing date refers to a completely missing date or to an incomplete date/partial date where parts are not available, e.g. missing month/day/year.
2. Missing start and end date will be imputed conservatively, i.e. missing values will be imputed in such a way that the duration of the AE is considered with the longest possible duration and such that, whenever the AE may potentially start after first IMP, the AE will be handled as a TEAE.
3. The missing start date and End date of AE will be imputed for the purpose of calculating treatment emergent status and assigning events to treatment periods using definitions given in the following table.

	Adverse event
Partial /Missing Start date	Missing day – If Adverse event start day is missing but month and year is present then Impute the 1st of the month unless month is same as month of first dose of study drug then impute first dose date.  Missing day and month – If adverse event start day and month are both missing but year is present then impute 1st January unless year is the same as first dose date then impute first dose date.  Completely missing – impute first dose date unless the end date suggests it could have started prior to this in which case impute the 1st January of the same year as the end date.  When imputing a start date, ensure that the new imputed date is sensible i.e. is prior to the end date of the AE.

	Adverse event
Partial /Missing End date	Missing day – If AE end day is missing but month and year are present then Impute the last day of the month unless month is same as month of last dose of study drug then impute last dose date.  Missing day and month – If AE has missing day and month but year is present then impute 31st December unless year is the same as first dose date then impute last

This document is confidential.

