Partial /Missing End date	
Missing day – If AE end day is missing but month and year are present then Impute the last day of the month unless month is same as month of last dose of study drug then impute last dose date.
 
Missing day and month – If AE has missing day and month but year is present then impute 31st December unless year is the same as first dose date then impute last dose date.
 
Completely Missing – need to look at whether the AE is still ongoing before imputing a date and also when it started in relation to study drug. If the ongoing flag is missing then assume that AE is still present (i.e. do not impute a date). If the AE has stopped and start date is prior to first dose date then impute the 1st dose date, if it started on or after first dose date then impute a date that is after the last dose date.

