**Statistical Analysis Plan**

Sponsor: Zogenix International Limited; Protocol No.: ZX008 Study 2 (ZX008-1501 and ZX008-1502)

	
dose date.
 
Completely Missing – need to look at whether the AE is still ongoing before imputing a date and also when it started in relation to study drug. If the ongoing flag is missing then assume that AE is still present (i.e. do not impute a date). If the AE has stopped and start date is prior to first dose date then impute the 1st dose date, if it started on or after first dose date then impute a date that is after the last dose date.

--	--------------------------------------------------------------------------------------------------------------------------------------------------------------------------------------------------------------------------------------------------------------------------------------------------------------------------------------------------------------------------------------------------------------------------------------------------------------------------

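### The imputation rules for incomplete AE dates can give an end date outside the recorded year or before onset, and their trigger for a missing start date can be read so that a possible on-drug event becomes non-TEAE

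*SAP*

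**What the plan says.** Both SAPs set the same principle above their imputation table (Study 2 SAP 6.4 and Study 1 SAP 6.1.7, handling of missing AE dates). Missing dates are to be filled so that "the duration of the AE is considered with the longest possible duration" and so that "whenever the AE may potentially start after first IMP, the AE will be handled as a TEAE". Item 3 gives the purpose: deciding treatment-emergent status and assigning events to periods.

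The rules at issue are:

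- **No start date at all:** "impute first dose date unless the end date suggests it could have started prior to this in which case impute the 1st January"; the year used is that in which the event ended.
- **End day missing:** "Impute the last day of the month unless month is same as month of last dose of study drug then impute last dose date".
- **End day and month missing:** "impute 31st December unless year is the same as first dose date then impute last dose date" (Study 1 SAP; the Study 2 SAP has the same rule).
- **Only plausibility check:** "When imputing a start date, ensure that the new imputed date is sensible i.e. is prior to the end date of the AE". It covers imputed start dates only.

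TEAE status depends on the start date, and AEs are collected through Visit 13 (Study 2 SAP 10.3; Study 1 SAP 6.4.1).

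**The concern.** The principle and the table beneath it do not agree. Two of the end-date rules can give dates that the record itself rules out: an end in a year other than the recorded one, or an end before a known onset. The rule for a fully missing start date rests on a phrase that can be read so widely that it overrides the TEAE default just above it.

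At stake are the TEAE and AESI incidence tables (for the start-date rule), the assignment of events to periods, and possibly the mean-duration tables planned for Study 2 (14.3.1.10, 14.3.1.11 and 14.3.1.18). The AESI list includes cardiac events, so classification should not be left to a programmer's reading.

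**Working it through.** The plan states no figure to reproduce here. The check applies the rules literally to constructed dates, which are assumptions chosen to lie within the planned schedule.

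**Inputs from the documents.** T+M is 98 days (Study 2 SAP 6.4). The taper lasts 8 days (2.7). Visit 12 is Study Day 99 and Visit 13 is Study Day 113 (2.8). The double-blind period is 16 weeks, or 112 days (6.5). There are about 40 subjects per arm (2.5).

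**1. Year-only end date.** The rule compares the recorded year with the first-dose year, then imputes the last dose date.
- First dose 10 Nov 2016, last dose 10 Nov 2016 + 111 days = 1 Mar 2017, AE end recorded only as 2016.
- The recorded year equals the first-dose year, so the imputed end is 1 Mar 2017. The record excludes that year.
- Exposure: a subject treated for L days crosses a year end with probability (L − 1)/365 if first doses are uniform over the year (assumption). L = 98 gives 97/365 = 27%; L = 112 gives 111/365 = 30%. This is the share who could meet the case, not an error rate. The case also needs an AE end date recorded as a year only.

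**2. End before onset, and shortened events.** In a subject who tapers, the last dose falls on about Study Day 98 + 8 = 106 (107 if counted from Visit 12 on Day 99). Visit 13 is Day 113, so about 6 to 7 days of AE collection follow the last dose.
- First dose 1 Mar 2018, last dose 14 Jun 2018 (Day 106), onset 17 Jun 2018 (Day 109).
- An end recorded as June 2018 is imputed as 14 Jun 2018, 3 days before onset. An end recorded only as 2018 gives the same date.
- An event with earlier onset that could have lasted past 14 Jun is also cut to that date, against the longest-duration principle.
- Subjects who enter the transition are dosed to about Day 14 after Visit 12 and have almost no such gap.

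**3. Start date fully missing.** First dose 15 Mar 2018, AE end 20 Apr 2018. Onset on drug was possible on any of 37 days (15 Mar to 20 Apr). A start imputed as the first dose date is counted here as a TEAE, as the default intends.

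| Reading of the trigger | Imputed start | Class |
|---|---|---|
| Literal: the end date does not exclude an earlier start | 1 Jan 2018 | non-TEAE |
| Narrow: the end date is before first dose | 15 Mar 2018 | TEAE |

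Under the literal reading the calendar also decides the class. First dose 15 Nov 2018 with end 20 Jan 2019 gives a start of 1 Jan 2019, which is a TEAE. The start-date check does not help, because 1 January precedes the end date in both examples.

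A related departure concerns fully missing end dates: "If the AE has stopped and start date is prior to first dose date then impute the 1st dose date". That is not the longest possible duration either.

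**The case against.** The strongest reply concerns the start-date rule. The clause says the end date must suggest an earlier start, which is more than failing to exclude one. On the literal reading every known end date triggers the exception, and the first-dose default is left only for events with no end date. A reading that nearly empties the main clause is weak, and the narrow reading agrees with item 2. This stands to the extent that misclassification is not certain. It does not remove the defect, because the narrow condition appears nowhere and the programmer must choose.

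Four further replies also stand:

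- End dates do not affect TEAE counts, and the one titration-period AE table (14.3.1.21) is defined by onset.
- Item 3 limits the stated purpose of imputation, and nothing says that imputed dates feed the duration tables. The Study 1 table list has no such table.
- All AEs are listed with TEAE status, and AESIs are listed separately, so a misclassified event would still be visible.
- The principle pulls two ways when the start is missing: longest duration favours an early start, TEAE status favours first dose.

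None of these replies defends an end date in a year the record excludes, or one that precedes onset.

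**Conclusion.** The rules should be corrected. The two end-date defects need no interpretation. The start-date defect is a trigger that can breach the SAP's own TEAE principle, depending on how it is programmed.

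The size is small. Only incomplete dates are affected, and the documents do not say how often they occur. Only the start-date rule can change TEAE or AESI incidence, by at most 1/40 = 2.5 points per subject, and only if that subject has no other event in the same row. The end-date rules can affect period assignment and, if imputed dates are used there, mean durations. Measured against a cap at Visit 13, the shortening after a planned taper is about a week, before visit windows.

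A reader might infer more than the documents support:

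- **That on-treatment events with no start date will be lost as non-TEAEs.** This follows only under the literal reading.
- **That about 30% of subjects will have wrong end dates.** That figure is only the share crossing a year end under uniform entry.
- **That the duration tables will contain negative values.** The SAPs do not say imputed dates enter them.

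**What to change.** Amend the table in Study 2 SAP 6.4, and the matching text in Study 1 SAP 6.1.7 if those analyses are rerun:

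- **Start fully missing:** impute 1 January of the end year only when the end date is before first dose; otherwise impute the first dose date. This gives TEAE status priority over longest duration where the two conflict, and the text should say so.
- **End date partial:** impute the last day of the recorded month or year, capped at Visit 13 or last contact and never before AE onset. Delete the branches that substitute the last dose date or test the first-dose year.
- State whether imputed dates enter the mean-duration tables.

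Applied to the examples, the year-only end becomes 31 Dec 2016. The June 2018 end becomes 21 Jun 2018 (Visit 13 at Day 113), after onset on 17 Jun. The event that ended 20 Apr 2018 starts on 15 Mar 2018 and is a TEAE.

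The cost is a few lines of SAP text and derivation code. The downside is that a few truly pre-treatment events may be counted as TEAEs, as the SAP's principle intends.

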**Statistical Analysis Plan**

Sponsor: Zogenix International Limited; Protocol No.: ZX008 Study 2 (ZX008-1501 and ZX008-1502)

	
dose date.
 
Completely Missing – need to look at whether the AE is still ongoing before imputing a date and also when it started in relation to study drug. If the ongoing flag is missing then assume that AE is still present (i.e. do not impute a date). If the AE has stopped and start date is prior to first dose date then impute the 1st dose date, if it started on or after first dose date then impute a date that is after the last dose date.

--	--------------------------------------------------------------------------------------------------------------------------------------------------------------------------------------------------------------------------------------------------------------------------------------------------------------------------------------------------------------------------------------------------------------------------------------------------------------------------

**6.5. Visit Windows**

The following rules will be used to window data into treatment periods for by treatment period tabulations. For all by-visit tabulations, the nominal visit as recorded on the CRF will be used.

Double Blind Treatment Period	
The Double-Blind Treatment Period start date is the date of first treatment, Study Day 1 (ie, the day after V3). The Double-Blind Treatment Period end date is the last date the patient was on study treatment.
 
The Double-Blind Treatment Period consists of 16 weeks from first treatment start date, which includes 2 weeks of Titration period, 12 weeks of Maintenance period and 2 weeks of Taper/Transition period; therefore the end date would be considered the date at Visit 13.
 
For subjects who discontinue early from the study, the double-blind treatment period end date will be the date at the early termination visit (Visit 12).

Titration Period	
The Titration Period covers the first 14 ± 4 days of treatment while subjects are titrated to their randomized dose. It begins on the first day of treatment (Study Day 1) and extends through Visit 6 (when the patient has reached their randomization dose). The Titration Period applies to all subjects including placebo recipients. If a subject withdraws from the study prior to treatment in the maintenance period, all safety assessments and events up to and including the date of study withdrawal will be tabulated in the titration period.

Maintenance Period	
The Maintenance Period covers the 12 weeks following the end of the titration period. It begins on the date of Visit 6 + 1 day and extends through the end of study/early termination visit (Visit 12).

Titration + Maintenance Period (T+M)	
The T+M period combines the Titration and Maintenance periods, beginning on the date of first treatment (Study Day 1) and extending to the end of study/end of treatment visit. The T+M period is considered the treatment period.

Taper/Transition Period	
The Taper/Transition period consists of 2 weeks starting from end of study/early termination visit (Visit 12) + 4 day.
 
For patients who are not entering into the open-label extension study, patients will gradually be tapered off of study medication.
 
For patients who are entering the open-label extension study, patients will enter the transition phase where all patients will be on a dose of 0.2 mg/kg/day at the end of this phase. The end date of this period is considered to be the date recorded at Visit 13.

This document is confidential.

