**Taper Period:**

Subjects who complete the Maintenance Period and were not continuing into the open-label extension study and subjects who discontinued from the study early were to be tapered off from study medication. Study medication was administered as equal doses BID in the morning and in the evening approximately 12 hours apart, with food. Each dose should have been separated by a minimum of 8 hours and a maximum of 12 hours. A missed dose of study medication may have been taken later up to 8 hours before the next scheduled dose; otherwise, the missed dose should not be given. IMP was administered using the oral dosing syringe provided.

In order to maintain the blind across all dose groups, all subjects who did not continue into the open-extension study participated in a dose-tapering procedure over the course of 8 days. On the first day of the tapering period subjects in the ZX008 0.8 mg/kg/day group decreased to a dose of ZX008 0.4 mg/kg/day BID (maximum 30mg/day). After 4 days at this dose level (Day 5), subjects randomized to the ZX008 0.8 mg/kg/day group decreased their dose to 0.2 mg/kg/day. Subjects in the ZX008 0.2 mg/kg/day group decreased their dose to placebo on the first day of tapering while doses in the placebo group remained constant throughout the tapering procedure. On Day 9, all subjects stopped taking study medication. The taper was expected to take a total of 8 days (Table 2). A new bottle of IMP was started by the subject at each level of the taper step.

Table 2. Taper Algorithm

Randomized Group	Taper Step 1 Day 1-4 after study completion or early termination	Taper Step 2 Days 5-8 after study completion or early termination

This document is confidential.

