**Transition Period:**

Subjects who completed the Maintenance Period and were continuing into the open-label extension study were to be transitioned from double-blind study medication to open-label ZX008 (Table 3). Study medication was administered as equal doses BID in the morning and in the evening approximately 12 hours apart, with food. Each dose should have been separated by a minimum of 8 hours and a maximum of 12 hours. A missed dose of study medication may have been taken later up to 8 hours before the next scheduled dose; otherwise, the missed dose should not be given. Study medication was administered using the oral dosing syringe provided.

All subjects entering the open-label extension study were transitioned from their blinded daily dose (placebo, 0.2 mg/kg/day, 0.8 mg/kg/day, or 30 mg/day) to the 0.2 mg/kg dose during the 2-week interval between Visits 12 and 13, without breaking the blind. The IWR system assigned two bottles of IMP to the subject, one for each step in the transition. A new bottle of IMP was started by the subject at each level of the transition step.

Table 3. Transition Algorithm

Dose Group in Double-Blind Study	Transition Step 1 Day 1-4 after Visit 12	Transition Step 2 Days 5-14 after Visit 12
ZX008 0.2 mg/kg/day	ZX008 0.2 mg/kg/day	ZX008 0.2 mg/kg/day
ZX008 0.8 mg/kg/day	ZX008 0.4 mg/kg/day	ZX008 0.2 mg/kg/day
Placebo	ZX008 0.2 mg/kg/day	ZX008 0.2 mg/kg/day
Note: maximum daily dose of ZX008 is 30 mg.		

Subjects who had been randomized to placebo increased their dose to 0.2 mg/kg/day beginning on Day 1 of the transition (the day following Visit 12.) Subjects who had been randomized to 0.2 mg/kg/day continued to receive that dose. Subjects who had been randomized to 0.8 mg/kg/day or were receiving the maximum dose of 30 mg/day decreased to a dose of ZX008 0.4 mg/kg/day, or a maximum of 30 mg/day. After 4 days at this dose level (Day 5), these subjects decreased their dose to 0.2 mg/kg/day. Subjects were to report to the clinic on Day 15 for enrollment into the open-label extension study.

Data from the Taper or Transition period will not be included towards the planned efficacy endpoints except where specified, but will be included in the safety analyses.

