### 10.3. Adverse Events

An AE is defined as any unfavorable and unintended sign (including an abnormal, clinically significant laboratory finding), symptom, or disease temporally associated with the use of a medicinal (investigational) product, whether or not considered related to the medicinal (investigational) product. The period of observation for adverse events extends from the time the subject gives informed consent until the end of the titration/transition period (Visit 13). For patients who continue into the open-label extension study, AEs of special interest will continue to be monitored for up to 6 months after the last dose of study medication.

A TEAE is defined as any AE that based on start date information occurs after the first intake of study treatment. Safety tables will present TEAE data by assigned treatment group through Visit 13. All other AEs occurring after enrollment and prior to the first administration of study treatment are defined as non-treatment emergent AEs (non-TEAEs).

AEs are categorized as related or unrelated. If the AE is thought to be definitely, probably or possibly related to study drug then it is to be categorized as related. Possibly or definitely unrelated is categorized as unrelated. Any missing relationship will be considered as "related."

The severity of AEs (whether nonserious or serious AEs) will be assessed by the investigator as follows:

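### The double-blind safety window has three conflicting end dates; in tables that use it, events after early termination are left out for dropouts while the same two weeks count for completers

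*SAP*

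**What the plan says.** The Double Blind Treatment Period row of Study 2 SAP Section 6.5 holds three statements about when the period ends.

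- General rule: "The Double-Blind Treatment Period end date is the last date the patient was on study treatment".
- Length: 16 weeks, "which includes 2 weeks of Titration period, 12 weeks of Maintenance period and 2 weeks of Taper/Transition period", and "therefore the end date would be considered the date at Visit 13".
- Early discontinuers: "For subjects who discontinue early from the study, the double-blind treatment period end date will be the date at the early termination visit" (Visit 12).

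Four other places in the same SAP bear on the days after an early-termination (ET) visit.

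- Section 2.7, Taper Period: "subjects who discontinued from the study early were to be tapered off from study medication". The taper takes 8 days. On its first day "subjects in the ZX008 0.8 mg/kg/day group decreased to a dose of ZX008 0.4 mg/kg/day", and this arm stays on ZX008 at a lower level for Days 5 to 8. The 0.2 mg/kg/day and placebo arms take placebo throughout.
- Section 2.7, end of Transition Period: Taper and Transition data stay out of the efficacy endpoints unless specified, "but will be included in the safety analyses".
- Section 6.5, Taper/Transition row: that period starts from the end-of-study or ET visit and ends at Visit 13.
- Section 10.3: "Safety tables will present TEAE data by assigned treatment group through Visit 13".

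None of these four makes an exception for dropouts. The Study 1 SAP has the same wording in Section 6.1.6, with the same counter-statements in Sections 3.3 and 6.4.1.

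**The concern.** Section 6.5 presents its rules as the ones used to place data into periods for by-period tabulations, so a programmer would take the double-blind window from there. Read that way, a completer is followed for harm for two weeks past Visit 12 and a dropout for none. Those two weeks include days on which dropouts from the 0.8 mg/kg/day arm, and only that arm, still take ZX008. A programmer working from Section 10.3 would keep the same events. The SAP does not say which section prevails.

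At stake are the outputs whose titles name the double-blind period. In Study 2 these are Table 14.3.1.1, whose overview includes serious and severe treatment-emergent adverse events (TEAEs) and TEAEs leading to death, and Tables 14.3.1.10 to 14.3.1.20. In Study 1 it is Table 14.3.1.1. Because the TEAE incidence summaries of Section 10.3 are limited to T+M, the double-blind tables are the main summary tables in which a taper event could appear at all.

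**Working it through.** **Inputs (Study 2 SAP).** Period lengths of 2, 12 and 2 weeks (Section 6.5). Visit 12 at Day 99 and Visit 13 at Day 113 (Tables 4 and 5). Taper of 8 days (Section 2.7). Post-dosing visit 2 weeks after completion or early termination (Section 2.3). Study 1 dropout 9/119 (Section 6.4). Planned 40 per arm (Section 2.5).

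**1. The plan's own figures.** 2 + 12 + 2 = 16 weeks = 112 days. Visit 13 minus Visit 12 is 113 − 99 = 14 days. 9/119 = 7.56%. All three reproduce.

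**2. The three end dates side by side**, taking a dropout whose ET visit is on Day t and who completes the taper.

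| Rule in Section 6.5 | Dropout | Completer who tapers | Completer in Transition |
|---|---|---|---|
| Last date on treatment | t + 8 | 99 + 8 = Day 107 | 99 + 14 = Day 113 |
| Visit 13 | t + 14 | Day 113 | Day 113 |
| ET visit | t | not applicable | not applicable |

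The three rules give a dropout three different dates. The first two also disagree by 6 days for a completer who tapers, so the ET sentence is not the only one that needs attention.

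**3. Which outputs can differ.** The incidence summaries in Section 10.3 (all, serious, by severity, related, leading to discontinuation) and the summary of adverse events of special interest are for T+M. That period closes at the end-of-study or end-of-treatment visit for completers and dropouts alike, so taper events fall outside it for both. Listings of deaths, serious events and discontinuations due to adverse events carry no period cut. That leaves the tables labelled double-blind.

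**4. Size for one dropout.** Days cut = 14, of which 8 (8/14 = 57%) are on taper medication. As a share of that dropout's own window extended to Visit 13, the cut is 14/(t + 14): 50% at t = 14, 22% at t = 49, 13.5% at t = 90. For a 0.8 mg/kg/day dropout, the share of time to the last taper dose that is cut is 8/(t + 8): 36%, 14% and 8%.

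**5. Size for an arm**, assuming 40 subjects and dropout d equal across arms.

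- Dropouts = 40d. Calendar days cut = 40d × 14. ZX008 days cut in the 0.8 arm = 40d × 8; in the other arms, 0.
- d = 5%: 2.0 dropouts, 28 days, 16 ZX008 days.
- d = 7.56%: 3.0 dropouts, 42 days, 24 ZX008 days.
- d = 15%: 6.0 dropouts, 84 days, 48 ZX008 days.

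Share of window days cut = 14d / [112(1 − d) + d(t + 14)]. With d = 0.0756 and t = 49: 1.06 / (103.5 + 4.8) = 1.0%. Counting only ZX008 days in the 0.8 arm: 24.2 / (40 × 108.3) = 0.6%. With d = 15% the first share is 2.0 to 2.1%, and with d = 20% it is 2.7 to 2.9% (t = 28 or 49).

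**The case against.** The strongest reply is that the plan already keeps these events. Section 10.3 counts any adverse event after first intake as treatment-emergent and tabulates through Visit 13. Section 2.7 puts taper data in the safety analyses, Section 10 reports safety over 16 weeks, and Section 2.3 gives early terminators the post-dosing visit. This stands to the extent that a reader might infer that taper events are simply dropped from safety reporting, and the documents do not support that. They show a contradiction, with loss only in tables where the 6.5 window prevails.

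A reader might also infer that serious events and deaths on 0.8 mg/kg/day are understated. That is not supported either. Deaths and serious events are listed for all enrolled subjects whatever the period, so only a count in a double-blind table could change. The overview counts subjects with at least one event, so a subject who left for tolerability will usually have been counted already; the count moves only if the first event of that category starts during the taper. A downward bias against that arm would also need its dropout rate, and Section 6.4 gives only the overall Study 1 figure.

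Finally, it is tempting to call all the cut days on-drug days. Taper medication covers 8 of the 14.

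What survives is that Section 6.5 is an explicit windowing rule, that it contradicts a sentence in its own cell, and that nothing tells the programmer to prefer Section 10.3 in the tables labelled double-blind.

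**Conclusion.** The point holds as an unreconciled contradiction. Section 6.5 gives three end dates for one period, and the ET rule clashes with the Taper text, the Taper/Transition row and Section 10.3. If the ET rule is applied, tables labelled double-blind follow dropouts for 14 fewer days after Visit 12 than completers. Among dropouts, only the 0.8 mg/kg/day arm loses days on ZX008.

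The consequence is small: about 3 subjects per arm and 24 ZX008 person-days in the 0.8 arm (16 to 48 for dropout of 5% to 15%), or about 1% of window days or less at the Study 1 rate. This assumes 40 per arm, equal dropout across arms, and Study 1 dropout carried over to Study 2. The direction of any net bias cannot be stated without per-arm dropout. It is still worth correcting because the affected tables count rare events, where one subject is 1/40 = 2.5% of an arm.

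**What to change.** In Study 2 SAP Section 6.5:

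- For safety tabulations, end the double-blind period for every subject at Visit 13, the post-dosing visit, or at last contact if that visit is not done.
- Delete the ET sentence. Delete the sentence on the last treatment date as well, or limit it to exposure; left in place, it would still conflict with Visit 13 for anyone who tapers.
- Tabulate events with onset after the ET visit in the Taper period, under the randomised arm.

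The cost is a short text edit and one derived date. Adverse events are already observed through Visit 13, so no new data are needed, and treatment is not touched. The downside is that double-blind event counts may rise slightly.

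Study 1 was reported in September 2017. Note the discrepancy in Section 6.1.6 of its SAP, or rerun its Table 14.3.1.1 with the common end date as a check.
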